1 SUMMARY

PS0011 is a multicenter, 48-week, double-blind, placebo-controlled, parallel-group extension study to assess the long-term safety, tolerability, and efficacy of bimekizumab in eligible adult subjects with moderate to severe chronic plaque psoriasis who complete PS0010. At Week 12 of PS0010, all eligible subjects continuing into PS0011 will undergo the PS0010 Week 12 study assessments and any additional PS0011 Baseline assessments, and will then receive their first dose of bimekizumab or placebo in PS0011.

During the Treatment Period, subjects will attend study visits at the study site every 4 weeks (Q4W) for study assessments and administration of bimekizumab or placebo by study site staff through Week 48. Any subject who does not achieve a Psoriasis Area and Severity Index (PASI) 75 response (defined as a 75% reduction in the PASI score from the Baseline of PS0010) at Week 12 or later in PS0011 will be withdrawn from study treatment and will return to complete the Early Withdrawal Visit assessments. Following completion or early withdrawal from the 48-week Treatment Period, subjects will return for a Safety Follow-Up (SFU) Visit 20 weeks after their last dose of bimekizumab or placebo in PS0011.

Subjects withdrawing early from the study will undergo the Early Withdrawal Visit assessments and will enter the SFU Period.

Subjects who received placebo or bimekizumab 64mg, 160mg, or 320mg loading dose + 160mg Q4W in PS0010 must achieve PASI90 response at Week 12 in PS0010 to enter the PS0011 extension study on the same treatment dose. Subjects who do not achieve PASI90 response at Week 12 in PS0010 while receiving placebo or bimekizumab 64mg Q4W will be assigned to receive bimekizumab 160mg Q4W on entering PS0011. Subjects who do not achieve PASI90 response at Week 12 in PS0010 while receiving bimekizumab 160mg or 320mg loading dose + 160mg Q4W will be assigned to receive bimekizumab 320mg Q4W on entering PS0011. Subjects who receive bimekizumab 320mg or 480mg Q4W in PS0010 will be assigned to receive bimekizumab 320mg Q4W on entering PS0011, regardless of their PASI90 response at Week 12 in PS0010.

Up to 240 subjects are anticipated to enroll in PS0011 at approximately 40 sites in Europe, Canada, and the US, with possible extension to other regions and countries as required in PS0010.

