5.4 Rationale for study design and selection of dose

PS0011 is a 48-week, double-blind, placebo-controlled, parallel-group extension study for eligible subjects who complete PS0010, a Phase 2b, randomized, double-blind, placebo-controlled, parallel-group, dose-ranging study in adult subjects with moderate to severe chronic plaque psoriasis. Because some PS0010 subjects may have severe disease, the treatment in PS0011 provides more time to respond to a potentially efficacious treatment. PS0011 also provides an opportunity for nonresponding PS0010 placebo subjects to receive bimekizumab. This study will allow the collection of further data on the long-term safety, tolerability, and efficacy of bimekizumab in this subject population.

The PS0011 design (Figure 5–1) allows PASI90 responders in PS0010 to continue their dose in PS0011, thus permitting these subjects to remain on the dose that resulted in this response after 12 weeks of initial treatment in PS0010. It also provides an opportunity for an increased dose among PS0010 nonresponders (ie, <PASI90). PASI90 was selected as the response criterion in PS0010 to ensure that a sufficiently high efficacy response was achieved. This type of dose escalation for those who do not achieve a desired response after 12 weeks is common in clinical practice.

Regardless of PASI90 response at Week 12 of PS0010, subjects who received the 2 highest doses of bimekizumab (320mg and 480mg Q4W) in PS0010 will begin PS0011 on the 320mg Q4W dose. For those subjects who do achieve PASI90 response, this will allow a continuation of the PS0010 dose for subjects initially receiving 320mg Q4W and a dose down for subjects originally randomized to the 480mg Q4W dose. Because bimekizumab 480mg Q4W is the highest dose evaluated in PS0010 and because it requires 3 injections, it will be of interest to evaluate whether these subjects can maintain response in PS0011 with the lower 320mg dose, allowing the blind to be maintained with the use of only 2 injections at each study administration visit.

To protect against the possibility of exposing subjects to an ineffective treatment for extended periods of time, subjects across all treatment groups who have not achieved PASI75 response at Week 12 or later in PS0011 will be withdrawn from study treatment. Because this withdrawal decision is based strictly on the PASI response and not on the original study treatment, it can be done in such a way that will not unblind subjects or Investigators.

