 - Subjects may remain in the study if the event is transient. If a subject has a Grade 2 laboratory abnormality, a retest is required within 1 to 2 weeks at a scheduled or unscheduled visit. If the repeat value is below Grade 2, the subject may receive the next scheduled study treatment. If the value on the repeat is still Grade 2 or above, a second repeat test must be performed and results made available prior to the next scheduled study treatment. If this second repeat value is still Grade 2 or above, the subject must be withdrawn.
10. Subject has active suicidal ideation as indicated by a positive response (“Yes”) to questions 4 or 5 or to the suicidal behavior questions of the “Since Last Visit” version of the self-rated electronic Columbia-Suicide Severity Rating Scale (eC-SSRS). The subject should be referred immediately to a Mental Healthcare Professional and must be withdrawn from the study.
11. Subjects with a HADS-D score ≥ 15 must be withdrawn. Any subject who develops a HADS-D score of >10 during the study should be referred immediately to a Mental Healthcare Professional for further evaluation and potential withdrawal by the Investigator.
12. Subject does not achieve PASI75 at Week 12 or later following study treatment in PS0011.
13. Subject experiences an AE as described below:
 - Any CTCAE Grade 3 and above adverse event (AE) that is assessed as related to study drug in the opinion of the Investigator
 - If the event is deemed to be not related to study drug by the Investigator, the subject may remain in the study after approval by the Medical Monitor.
 - Any CTCAE Grade 2 event that is evaluated as related to study drug in the opinion of the Investigator, is persistent, and falls into any of the following System Organ Classes (SOCs): “Blood and lymphatic disorders,” “Cardiac disorders,” or “Vascular disorders.”
 - Persistent is defined as lasting 28 days or more, which spans at least 2 scheduled injections.

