14.6 Planned efficacy analyses

Efficacy variables will be summarized based on the FAS. The summaries described in this section will provide data on maintenance of effect of study treatment over 48 weeks.

Responder efficacy variables (PASI75, PASI90, PASI100, IGA, and DLQI score of 0 or 1) will be summarized descriptively using counts and percentages by scheduled visit and PS0010/PS0011 treatment group. The PASI responder variables will be derived relative to both the PS0010 Baseline and the PS0011 Baseline with responder rates being presented side-by-side in applicable summary tables. Missing data will be handled by using nonresponder imputation (NRI), meaning that subjects that discontinue early or who have missing data at a given time point are imputed as though they did not achieve the given response. Supportive summaries will be based on observed case data.

Continuous efficacy variables based on the change from Baseline (PASI, DLQI, BSA, mNAPSI, PSSI, PGADA, SF-36, and HADS) will be summarized using descriptive statistics by scheduled visit and PS0010/PS0011 treatment group. The table presentations will display descriptive statistics for the PS0010 Baseline, followed by descriptive statistics for the observed, change from PS0010 Baseline, and change from PS0011 Baseline results by scheduled visit for PS0011. Figures for selected variables will also be generated in order to demonstrate the kinetics of response over time. Missing data will be handled by using multiple imputation (MI) via the Markov-Chain Monte Carlo (MCMC) method. Supportive summaries will be based on observed case data.

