3.3 Mapping of assessments performed at early study withdrawal visit

Study assessments at an early withdrawal visit where the early withdrawal visit date matches the visit date of a scheduled visit will be summarized at the scheduled visit with the same visit date. Premature withdrawal visit assessments that do not have a scheduled visit with a matching date will be assigned to the next scheduled site visit following the last visit where assessments were available. The only exception to this rule is for anti-Bimekizumab (BKZ) antibody assessments, where all premature withdrawal visit assessments will be assigned to the next scheduled visit at which anti-BKZ antibodies are assessed.

All by-visit summaries will contain nominal visits only. Unscheduled visits will not be mapped to scheduled visits.

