4.2.2 Handling missing data for the efficacy analyses

For the planned efficacy analysis, missing responder data will be imputed using non-responder imputation (NRI). That is, subjects that discontinue study medication early or who have missing data at a given time point will be counted as non-responders. Summaries based on observed case data will also be prepared.

Continuous efficacy variables will be imputed using multiple imputation (MI) via the Markov-Chain Monte Carlo (MCMC) method. Summaries based on observed case data will also be prepared.

The MI procedure for continuous efficacy variables (based on MCMC) will be applied as follows:

1. Create a dataset, one for each treatment group, of subjects with observed values and those needing estimation by multiple imputation. The missing values in each dataset will be filled in using the MCMC method with a total of 100 sets of imputations being performed. Values at Baseline and at each post-Baseline visit will be included in the imputation model in chronological order with prior biologic exposure and region as factors. The resulting datasets for each treatment arm will be combined into one complete dataset based on each of the 100 imputations.

Note: The imputation model based on the MCMC method will only allow continuous variables in the imputation model. Therefore, prior biologic exposure and region will be re-coded as indicator variables (with values of 0 or 1 for each level of the variable). In order to achieve model convergence, prior biological exposure may be dropped from the model, if convergence is still not obtained then region may also be dropped from the model.

2. The relevant change from Baseline (or percent change from Baseline) values will then be derived based on the imputed datasets and will be summarized by imputation.
3. The summary statistics from each of the 100 imputed datasets will be combined for the calculation of means and standard deviations using Rubin's rules, which account for the uncertainty associated with the imputed values (Rubin, 1987). This will be done using SAS PROC MIANALYZE. For calculation of other descriptive statistics such as the median, min and max, Rubin's rules do not apply. Multiple imputation estimates will be computed by simply averaging the estimates from the $m = 1, \dots, M$ independent repetitions of the imputation algorithm:

$$\bar{\theta} = \frac{1}{M} \sum_{m=1}^M \hat{\theta}_m$$

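### Observed-case responder tables after Week 12 are conditional on passing the PASI75 withdrawal rule, so they cannot serve as support for the NRI results

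*Protocol*

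**What the plan says.** Criterion 12 in Protocol 6.3 requires withdrawal if: "Subject does not achieve PASI75 at Week 12 or later following study treatment in PS0011". Protocol 5.4 makes the scope explicit: "subjects across all treatment groups who have not achieved PASI75 response at Week 12 or later in PS0011 will be withdrawn from study treatment". The Protocol Summary fixes the reference for PASI75: "defined as a 75% reduction in the PASI score from the Baseline of PS0010". A subject who fails then has only the Early Withdrawal and Safety Follow-Up visits left.

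For responder variables the main handling of missing data is NRI. SAP 4.2.2 puts it as: "subjects that discontinue study medication early or who have missing data at a given time point will be counted as non-responders". Beside it, Protocol 14.6 says: "Supportive summaries will be based on observed case data", and SAP 4.2.2 says: "Summaries based on observed case data will also be prepared". Neither document restricts or annotates these tables for criterion 12, and the design summary in SAP 2.3.2 does not mention the PASI75 rule.

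Two other places matter. Under SAP 3.3, an Early Withdrawal visit whose date matches no scheduled visit "will be assigned to the next scheduled site visit following the last visit where assessments were available". SAP 10.1.2.2 specifies the IGA shift table on observed data, with no NRI counterpart.

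**The concern.** Ordinary dropout may or may not relate to response. Here the data are absent because the response variable fell below a threshold. An observed-case rate at a later visit is the chance of response given PASI75 at every earlier visit from Week 12. It is a different quantity from the one NRI reports, so agreement or disagreement between the two says nothing about how robust the NRI result is.

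The secondary objective is efficacy over 48 weeks, and Protocol 14.6 presents these summaries as showing maintenance of effect. Selection of this kind can make maintenance look better than it is and groups look more alike than they are.

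**Working it through.** **Plan's own figure.** There is none to reproduce. The study is descriptive, and the ceiling of 240 subjects is carried over from PS0010.

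**Inputs from the documents.** Visits every 4 weeks; rule applied at each visit from Week 12 to Week 48 against PS0010 Baseline; NRI and Early Withdrawal mapping as above.

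**Assumptions, not in the documents.** True rates constant over visits: PASI75 60% and 90%, PASI90 40% and 75%. Within-subject correlation ρ from 0 to 0.9, and no other dropout.

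**Model.** y = b + e, with b ~ N(0, ρ) per subject and e ~ N(0, 1 − ρ) per visit. PASI75 response if y < z(p75) and PASI90 response if y < z(p90). 400,000 simulated subjects per setting.

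**Formula.** Observed-case PASI75 at a visit = P(response now and at all earlier visits from Week 12) / P(still observed now). NRI has the same numerator over everyone.

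**PASI75 at Week 48 (true 60% / 90%), observed cases, in %:**

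| ρ | Early Withdrawal on the failing visit's date | Mapped to next visit, response reassessed | Mapped to next visit, always a failure |
|---|---|---|---|
| 0 | 59.8 / 90.0 | 60.0 / 90.0 | not consistent with ρ = 0 |
| 0.5 | 92.4 / 97.1 | 91.8 / 97.0 | 84.8 / 94.2 |
| 0.7 | 95.7 / 98.4 | 95.3 / 98.3 | 91.3 / 96.7 |
| 0.9 | 98.3 / 99.4 | 98.1 / 99.3 | 96.5 / 98.7 |

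In the same-day column at ρ = 0.7, 26.6% of the 60% group are still observed at Week 48 and 25.5% respond. The observed-case rate is about 25.5 / 26.6 ≈ 96%, while NRI is 25.5%.

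**When it starts.** At Week 12 the failing value is itself observed, so the rate is correct. With a same-day Early Withdrawal visit, 60% appears at Week 16 as 73.2, 79.5 and 88.5% (ρ = 0.5, 0.7, 0.9). With mapping and reassessment, Week 16 stays at 60% and those same values appear at Week 20. If the mapped visit is always a failure, Week 20 shows 58.5, 68.5 and 82.4%, so at ρ = 0.5 the inflation starts later still.

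**PASI90 at Week 48 (true 40% / 75%, difference 35 points), same-day Early Withdrawal:**

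| ρ | Observed case, % | Difference, points | NRI, % |
|---|---|---|---|
| 0.5 | 79.1 / 88.4 | 9.3 | 13.2 / 54.2 |
| 0.7 | 83.5 / 90.4 | 6.9 | 22.2 / 63.2 |
| 0.9 | 84.4 / 90.8 | 6.4 | 34.8 / 72.5 |

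**Hand check at full persistence.** Failures leave once and nobody else fails. Observed-case PASI75 is then 100% in both groups, and observed-case PASI90 is P90/P75: 0.40 / 0.60 = 66.7% and 0.75 / 0.90 = 83.3%, a difference of 16.7 points. PASI90 has no general pull to 100%.

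**Tables against PS0011 Baseline.** A subject with PASI 20 at PS0010 Baseline and a steady 4 afterwards is at (20 − 4) / 20 = 80% and stays in. Against PS0011 Baseline the improvement is (4 − 4) / 4 = 0%. Those tables need not approach 100%.

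PASI100, IGA and DLQI 0/1 were not simulated. They are subject to the same selection, but no size is claimed for them.

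**The case against.** The strongest reply is that the main results are protected. NRI keeps every subject in the denominator and is specified for the PASI, IGA and DLQI 0/1 response tables and for the subgroup tables. No inference is planned, PS0011 is not randomised, and groups are formed largely by PS0010 response. All of this stands, and it limits the point to supportive tables and the IGA shift table.

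A reader might infer that every observed-case table rises to 100% and erases dose differences whatever the true response. The documents do not support that. There is no effect at zero correlation, the secondary variable PASI90 keeps part of its difference, and PS0011-Baseline tables use another reference. A first failure is counted at its failing visit, and possibly once more under SAP 3.3. The efficacy tables are also split by PS0010 Week 12 PASI90 status, which the single-rate model ignores. Where the true rate is already near 100% there is little room for inflation.

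It can also be said that discontinuation reasons are already summarised (SAP 5.1). That summary is planned by PS0011 treatment group and not by visit, so it cannot be used to correct an observed-case table by PS0010/PS0011 group.

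Lastly, the remedy might look like NRI again. It differs: only criterion 12 withdrawals become failures, while data missing for other reasons stay out. The contrast with NRI then shows how much of the NRI result comes from unrelated missingness.

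**Conclusion.** The concern holds for the observed-case responder tables after Week 12. With moderate to high persistence (assumed ρ of 0.5 to 0.9), a true 30-point PASI75 difference at Week 48 shrinks to between 1.1 points (99.4 − 98.3) and 4.7 points (97.1 − 92.4) with same-day Early Withdrawal. If every mapped Early Withdrawal visit counts as a failure, the range is 2.2 (98.7 − 96.5) to 9.4 points (94.2 − 84.8). A true 35-point PASI90 difference shrinks to about 6 to 9 points in the same-day case.

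These sizes rest on assumed rates, a constant true response and no other dropout; the direction follows from the rule whenever response persists within subjects. The NRI analysis is not biased by this selection, and nothing here should be read as saying that it is. Following the plan as written would still produce supportive tables that cannot do their job, so the SAP should be changed rather than merely annotated.

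**What to change.** In SAP 4.2.2, for supportive summaries of responder variables against PS0010 Baseline, count a subject withdrawn under criterion 12 as a non-responder at every later scheduled visit, and leave out only data missing for other reasons. At the failing visit, PASI below 75 already implies non-response for PASI90 and PASI100; for IGA and DLQI 0/1 the rule is a convention and should be stated as one.

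If a pure observed-case table is also kept, label it as conditional on passing the PASI75 rule and do not use it to compare groups. Show the number withdrawn under criterion 12 by visit and PS0010/PS0011 group. Put the same footnote on the observed-case tables of continuous variables and on the IGA shift table.

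The cost is a sentence in the SAP, a footnote and a row of counts; the eCRF already records the primary reason for withdrawal. The supportive rates will be less favourable and will sit closer to NRI.

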6.3.1 PDILI IMP discontinuation criteria

Subjects with PDILI must be assessed to determine if investigational medicinal product (IMP) must be discontinued. In addition, all concomitant medications and herbal supplements that are not medically necessary should also be discontinued.

The PDILI criteria below require immediate and permanent discontinuation of IMP:

- Subjects with either of the following:
 - ALT or AST $\geq 5xULN$
 - ALT or AST $\geq 3xULN$ and coexisting total bilirubin $\geq 2xULN$
- Subjects with ALT or AST $\geq 3xULN$ who exhibit temporally associated symptoms of hepatitis or hypersensitivity. Hepatitis symptoms include fatigue, nausea, vomiting, right upper quadrant pain or tenderness. Hypersensitivity symptoms include fever (without clear alternative cause), rash, or eosinophilia (ie, $>5\%$).

The PDILI criterion below allows for subjects to continue on IMP at the discretion of the Investigator.

- Subjects with ALT or AST $\geq 3xULN$ (and $\geq 2x$ baseline) and $<5xULN$, total bilirubin $<2xULN$, and no eosinophilia (ie, $\leq 5\%$), with no fever, rash, or symptoms of hepatitis (eg, fatigue, nausea, vomiting, right upper quadrant pain or tenderness).

Evaluation of PDILI must be initiated as described in Section 9.7.1. If subjects are unable to comply with the applicable monitoring schedule, IMP must be discontinued immediately.

Investigators should attempt to obtain information on subjects in the case of IMP discontinuation to complete the final evaluation. Subjects with PDILI should not be withdrawn from the study until investigation and monitoring are complete. All results of these evaluations and observations, as well as the reason(s) for IMP discontinuation and subject withdrawal (if applicable), must be recorded in the source documents. The eCRF must document the primary reason for IMP discontinuation.

7 STUDY TREATMENT

7.1 Description of investigational medicinal product

The IMP used in this study are bimekizumab and placebo.

Bimekizumab will be supplied as a clear to opalescent, colorless to slightly brown, sterile, preservative free solution in 2mL Type I, colorless glass vials (1.0mL extractable volume) closed with a rubber stopper and sealed with an aluminum cap oversealed [REDACTED]

Placebo will be supplied as 0.9% sodium chloride aqueous solution (physiological saline, preservative free) of pharmacopoeia (USP/Ph.Eur) quality appropriate for injection.

Further details of the study medication and specifications are provided in the IMP Handling Manual.

7.2 Treatments to be administered

During the Treatment Period, all subjects will receive bimekizumab or placebo Q4W administered sc (refer to [Figure 5–1](#) for further details).

Subjects who received placebo or bimekizumab 64mg, 160mg, or 320mg loading dose + 160mg Q4W in PS0010 must achieve PASI90 response at Week 12 in PS0010 to enter the PS0011 extension study on the same treatment dose. Subjects who do not achieve PASI90 response at Week 12 in PS0010 while on these treatments will be assigned to receive bimekizumab 160mg or 320mg Q4W at Baseline in PS0011 as follows:

- Subjects receiving placebo and bimekizumab 64mg Q4W in PS0010 will be assigned to bimekizumab 160mg Q4W in PS0011.
- Subjects receiving bimekizumab 160mg Q4W and 320mg loading dose + 160mg Q4W in PS0010 will be assigned to bimekizumab 320mg Q4W in PS0011.

Subjects who receive bimekizumab 320mg or 480mg Q4W in PS0010 will be assigned to receive bimekizumab 320mg Q4W on entering PS0011, regardless of their PASI90 response at Week 12 in PS0010.

The study medication is to be administered in the clinic by study site staff as 2 sc injections for all study treatments in PS0011. Suitable areas for sc injections are the lateral abdominal wall and upper outer thigh. Injection sites should be rotated, and injections should not be given into areas where the skin is tender, bruised, red, or hard.

The minimum time between doses should be no less than 24 days and no more than 32 days for Q4W dosing.

An IMP Handling Manual will be provided to each site containing instructions regarding drug preparation and dosing.

